#### Randomisation and Device Fitting

Following completion of Baseline activities, participants will be randomly assigned to one of two groups, to begin the four-week crossover trial:

- Group 1 (ALD-Aided): Start with the device for the first two weeks; followed by
  usual care for the following two weeks. Allocated participants will have the
  device appropriately fitted for immediate use upon leaving site (for two weeks).
- Group 2 (Usual Care): Allocated to usual care for the first two weeks before starting with the device for the following two weeks. Although the participants allocated to Group 2 will have the remote microphone ALD appropriately fitted at Baseline (e.g., to ensure compatibility with current hearing aids if required and to perform part of the CNC Baseline test), they will not leave the site with the device until after the two-week (usual care) period.

# **Support and Training**

Participants and caregivers will be provided with training resources on how to use their remote microphone ALD in a range of situations and how to access support if required. In addition to support and training on ALD use by the research team, participants/carers will be provided with a helpline number and access to video support on ALD use from the manufacturer (Phonak, a Sonova Company).

Participants will also be instructed on how to complete their diary of ALD use and completion of the other questionnaires remotely using the REDCAP ePRO system.

#### Week 2 Visit (Crossover)

The Week 2 visit will take place at the trial site 14 days (+/- 3 days) following Baseline. **Week 2 Assessments/Activities** will consist of:

- Verbal Re-confirmation of Consent (agreement to continue participation).
- CNC test\* (completed in two conditions –ALD-Aided & non-ALD-Aided; test order to be the same as at Baseline)
- Participant completed questionnaires: SSQ-12, Tolerability Acceptability and Satisfaction\*, and SUS\*, IOI-HA (all applicable participants i.e., hearing-aid users)
- Review of any Adverse Events, Undesirable Effects and Technical Issues\*
- Review of Diary Data (compliance)\*
- Support and Training as required

#### Device Removal/ Re-Fit for Use

Following completion of the first two-week period, participants will 'crossover' treatment groups for the second two-week period to complete the crossover trial:

- Group 1 (ALD-Aided): Participants will return the device to site and undergo two weeks of usual care.
- Group 2 (Usual Care): Participants will have the device appropriately fitted at sitefor two weeks of use.

\* If applicable- ALD-Aided group only

#### Week 4 (End of Crossover / Start of Trial Extension Phase)

The Week 4 visit will take place at the trial site 14 days (+/- 3 days) following the Week 2 visit.

#### Week 4 Assessments/Activities will consist of:

- Verbal Re-confirmation of Consent (agreement to continue participation).
- CNC test\* (completed in two conditions— ALD-Aided & non ALD-Aided; test order to be the same as at Baseline)
- Participant completed questionnaires: SSQ-12, Tolerability Acceptability and Satisfaction\*, and SUS\*, IOI-HA (all applicable participants i.e., hearing aid users)
- Review of any Adverse Events, Undesirable Effects and Technical Issues\*
- Review of Diary Data (compliance)\*
- Support and Training as required

#### Device Re-Fit for Use - for the Trial Extension

Following completion of the crossover trial:

- Group 1 (ALD-Aided): Participants will have the device appropriately re-fitted at site for a further 20 weeks of use.
- Group 2 (Usual Care): Participants will return to site, where they will be reviewed for continued use of the device (if required) for a further 20 weeks.

#### Weeks 8, 12 & 16 Monthly Follow-ups (Optional)

Participants will be offered monthly follow-ups with the trial team (remotely) to check on progress and report on any issues experienced. Follow-ups may be via telephone, video call, or email correspondence (depending upon participant preference). Monthly follow-ups are optional and will be based on participant preference. Participants will also be free to contact the trial team on an ad-hoc basis if they have any questions or issues to report.

\* If applicable- ALD-Aided group only

#### Week 24

The Week 24 visit will take place at the trial site 20 Weeks (140 days) (+/- 14 days) following the Week 4 visit.

Week 24 Assessments/Activities will consist of:

- Verbal Re-confirmation of Consent (agreement to continue participation).
- Collection of updated medical history, medications and demographics
- LiSN-S test
- CNC test\* (completed in two conditions –ALD-aided & non-ALD aided; test order to be the same as at Baseline)
- Participant completed questionnaires: Tolerability Acceptability and Satisfaction, SUS, IOI-HA (if applicable), SSQ-12, MFIS, CPIB, SPaRQ, LIFE-H (Short Form), WHOQOL-BREF
- Caregiver completed questionnaire (if applicable): SOS-HEAR
- Newcastle Mitochondrial Disease Adult Scale (NMDAS)
- Clinical review of medical notes and collection of updated existing medical information and previous results (see Baseline visit for details)
- Review of any Adverse Events, Undesirable Effects and Technical Issues
- Review of Diary Data (compliance)
- Feedback on trial participation. The participant will be asked to provide feedback on their experience of the trial. This will be optional and participants do not need provide feedback if they do not wish to do so.

#### **Device Removal**

Following completion of the End of Trial visit:

• All participants will return their devices and return to usual care.

#### \* Note on Atkin & Fisher's articulation survey and CNC tests

These assessments will be audio recorded and the recordings stored so that scores can be checked and, if applicable, verified by independent assessors during the analyses stage. Audio recordings will be de-identified for storage and analyses purposes (utilising unique participant ID only). Consent will be obtained from participants to use these audio recordings in future research.

#### **End of Study**

The End of Study for each participant will be completion of the required assessments and activities at Week 24 (Visit 4) and returning the device. The overall end of study will be defined as completion of data collection, data cleaning and data analyses.

#### Withdrawal Visit (if required)

Participants who withdraw, or are withdrawn, from the trial at any point following randomisation will be invited to attend a withdrawal visit.

At this visit the following assessments/activities will take place:

- Return of the ALD (if applicable- if a participant withdraws during the non-ALD-Aided phase of the crossover there will be no ALD to return and the withdrawal visit may be completed remotely).
- Review of reason for withdrawal.
- Review of any Adverse Events, Undesirable Effects and Technical Issues
- Review of Diary Data (compliance)
- **Feedback on trial participation.** The participant will be asked to provide feedback on their experience of the trial. This will be optional and participants do not need provide feedback if they do not wish to do so.
- *If appropriate,* participants will be asked to re-complete follow-up trial questionnaires (optional).

# **SCHEDULE OF EVENTS**

Trial Assessments	Visit 1 (Trial site)		Visit 2 (Site)	Visit 3 (Site)	Follow up (Remote)	Visit 4 (Site)	Withdrawal Visit (Site)	
	Screen	ing	Baseline		End of crossover/			, ,
	Newcastle University	Ne	e1Hear	Crossover	Start of observation	Observation	End of Trial	As applicable
	Week 0		Week 2 +/- 3 days	Week 4 +/- 3 days	Monthly +/- 7 days	Week 24 +/- 14 days		
Informed Consent	Х							
Medical History	Х						X	
Medication Review	Х						X	
NMDAS (or collection of results from existing NMDAS)	Х						X	
Demographics	Х						X	
Atkin & Fisher's Articulation Survey	Х							
Speech-in-noise (SiN) tests	Х							
Pure-tone-Audiometry	Х							
LiSN-S Test		Х					X	
Eligibility Confirmation		Х						
Re-confirm Consent			Х	X	Х	Х	X	
Assistive Listening Device (ALD) Fitted			X 	X 	X (1 & 2)			
CNC Test *			Х	X	Х		X	
Speech, Spatial & Qualities of Hearing Scale (SSQ-12)			Х	X	Х		X	X (†)
MFIS, CPIB, SPaRQ, LIFE-H (Short Form), WHOQOL-BREF, & SOS-HEAR ‡			Х				Х	X (†)
Randomisation			Х					
Tolerability Acceptability & Satisfaction Questionnaire, SUS, IOI-HA ‡				X	Х		X	X (†)
Review of any Adverse Events, Undesirable Effects & Technical Issues				X	Х	Х	X	X
Review of Diary Data (compliance)				X	Х	Х	X	X
Clinical review of medical notes/collect relevant clinical information			Х				X	
Technical Support (from research team and Phonak/Sonova)			Х	X	Х	Х	X	
Return ALD							X	Χ
Participant Feedback (optional)							Х	Χ

\* Completed in 2 conditions (ALD-Aided and non-ALD-Aided); test order randomly allocated to participants at Baseline and the same order repeated at each visit

 Group 1: ALD-Aided for the first 2 weeks (will have tolerability, usability and satisfaction reviewed at Week 2 visit and will record AEs and compliance for first 2 weeks)

 Group 2: Usual care (non-ALD-Aided) for the first 2 weeks (will have tolerability, usability and satisfaction reviewed at Week 4 visit and will record AEs and compliance from weeks 2-4)

(1 & 2) Group 2 who used the ALD in the preceding 2 weeks will continue to use the device, Group 1 will have the device re-fitted and commence use again

<sup>‡Note on Questionnaires: After Baseline, participants will be able to complete their questionnaires via REDCAP. Relevant questionnaires will be enabled in REDCAP for completion for three days prior to the trial visit. Checks will be undertaken at the visit to ensure completion and completion on paper offered during the visit if needed.

f) If appropriate, participants will be asked to re-complete follow-up trial questionnaires upon withdraw (optional).

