#### 1) Four-week randomised, AB/BA crossover trial

Participants will be randomly allocated (1:1 ratio) to one of two sequences:

- Group 1: ALD-Aided (2 weeks), followed by usual care (non-ALD-Aided)
   (2 weeks); or
- o Group 2: Non-ALD-Aided (2 weeks), followed by ALD-Aided (2 weeks)

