# ADVERSE EVENT & ADVERSE INCIDENT REPORTING

#### **Adverse Events and Serious Adverse Events**

Due to the nature and purpose of the trial, only adverse events relating to the following will be reported for each participant:

- Hearing and ear health (including any ear infections)
- Hearing-aid use (where applicable)
- ALD use
- Events occurring during, or as a direct result of, trial visits/assessments.

Such adverse events will be documented in the participant medical notes recording causality and severity. They will also be recorded on the trial adverse event log. AEs will be followed up until resolution or until stabilisation (if complete resolution is not anticipated).

A Serious Adverse Event (SAE) for this trial will be defined as an adverse event (as requiring reporting above), which occurs and also meets the following criteria:

- Results in death
- Is life-threatening\*
- Requires inpatient hospitalisation or prolongation of existing hospitalisation
- Results in persistent or significant disability/incapacity
- Consists of a congenital anomaly or birth defect
- Other important medical events that jeopardise the participant or require intervention to prevent one of the above consequences

\*Life-threatening refers to an event in which the participant was at immediate risk of death at the time of the event; it does not refer to an event which hypothetically might have caused death if it were more severe.

In the event of a SAE, the Sponsor, The Newcastle upon Tyne Hospitals NHS Foundation Trust, will be notified immediately by email (within 24 hours of site awareness of the event) and the following details provided:

- Participants Unique Trial ID number
- Event Title and Description (including details of severity)
- Expedited Reporting Criteria
- Date of Event Onset
- Date of Site Awareness
- Causality (i.e. whether related to trial participation or trial procedures) This
  needs to be confirmed by the PI or delegated investigator who is medically
  qualified.
- Expectedness (if related to a trial procedure whether this is an 'expected' event)- This also needs to be confirmed by the PI or a delegated investigator who is medically qualified
- Action Taken
- Outcome/Current Status
- Resolution Date (if applicable)

If complete information is not available or if a PI/Investigator cannot be obtained within 24 hours the SAE report should be submitted as incomplete in the first instance and the missing details provided at the earliest opportunities.

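### Scheduled adverse-event review in the crossover is limited to ALD-aided periods, contrary to Table 1, the adverse-event section and the withdrawal visit, so usual-care events are captured only unsystematically

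*Protocol*

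**What the plan says.** The randomised phase is an AB/BA crossover in which each participant has two aided and two usual-care weeks. For Group 2 the order is "Group 2: Non-ALD-Aided (2 weeks), followed by ALD-Aided (2 weeks)"; Group 1 has the reverse.

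**Places that limit AE review to aided periods**
- The Week 2 and Week 4 visit lists include "Review of any Adverse Events, Undesirable Effects and Technical Issues" with an asterisk. The footnote to each list defines the asterisk as "If applicable- ALD-Aided group only".
- Schedule of Events, footnote (1): Group 1 "will record AEs and compliance for first 2 weeks".
- Schedule of Events, footnote (2): Group 2 "will record AEs and compliance from weeks 2-4".

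**Places that do not**
- Table 1 (Outcome Measures) has participants report AEs, undesirable effects and technical issues at every follow-up and also ad hoc.
- Adverse Events and Serious Adverse Events: "only adverse events relating to the following will be reported for each participant". The list begins with "Hearing and ear health (including any ear infections)" and also includes hearing-aid use and events arising from trial visits or assessments. No period is excluded.
- The Schedule of Events row for AE review has an unqualified mark at Weeks 2 and 4.
- The withdrawal visit includes AE review without an asterisk, and its text expressly foresees withdrawal during the unaided phase.

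Device-related adverse and undesirable effects are one of the measures under the primary objective. The Statistics section plans a mainly descriptive summary of the tolerability data.

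**The concern.** Staff cannot follow both sets of instructions. If they follow the visit lists and footnotes, a participant who has just finished usual care is not asked about ear, hearing-aid or visit-related events, although the AE section wants those events for everyone.

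The stake is attribution. The AE section requires causality to be recorded, and the primary measure counts effects judged to be device related. That judgement is easier when the same question has been asked, at the same interval, with and without the device. It is harder when an event that begins after device removal is first asked about months later, after the participant has been using the device again.

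**Working it through.** The protocol states no figure on this point, so there is none to reproduce. The check is a comparison of the text plus simple exposure arithmetic.

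**1. Who is reviewed when, if the restriction is followed**

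| Visit | Group 1 | Group 2 |
|---|---|---|
| Week 2 | reviewed (just aided) | not reviewed (just usual care) |
| Week 4 | not reviewed (just usual care) | reviewed (just aided; footnote gives weeks 2-4) |
| Weeks 8, 12, 16 | optional contact | optional contact |
| Week 24 | reviewed | reviewed |

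- Group 1: the gap between guaranteed reviews runs from Week 2 to Week 24, which is 24 − 2 = 22 weeks. Two of these weeks are usual care and 20 are renewed device use.
- Group 2: the device is fitted and the CNC test is done at Baseline, so a visit-related event can arise in weeks 0-2. Those weeks lie outside the recording window in footnote (2).

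**2. Exposure without scheduled review** (12 recruited; 10 completers in brackets)
- Usual-care person-weeks: 12 × 2 = 24 (10 × 2 = 20).
- Crossover person-weeks: 12 × 4 = 48 (40). Share: 24/48 = 50%.
- Whole-trial person-weeks: 12 × 24 = 288 (240). Share: 24/288 = 8.3%.

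**3. What review of the usual-care period might show**

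The protocol gives no background event rate, so the risks per two weeks below are assumptions. Expected participants with an event = 12p. Chance of at least one = 1 − (1 − p)^12.

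| Assumed p | Expected among 12 | Chance of at least one |
|---|---|---|
| 2% | 0.24 | 22% |
| 5% | 0.6 | 46% |
| 10% | 1.2 | 72% |
| 20% | 2.4 | 93% |

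The yield could be anything from probably nothing to a couple of participants.

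**4. Could it support a formal comparison?**

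In an exact two-sided McNemar test, d discordant pairs all in one direction give p = 2 × 0.5^d. Five pairs give 0.0625 and six give 0.031, so at least six are needed. With 12 participants, and aided and unaided events taken as independent within a participant, power is about 4% for 30% versus 10% and about 32% for 50% versus 10%. The extra data would be descriptive context only.

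**The case against.** The strongest reply is that the primary objective concerns the device. Its AE component is device related, the usability scale and the ALD diary have no meaning without the device, and the analysis is descriptive. Causality is judged event by event, and usual care is only 8.3% of planned follow-up. Footnotes (1) and (2) do not contain the word only, and AEs that begin in an aided period are followed to resolution or stabilisation.

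Much of this stands, and it rules out several stronger readings that a reader might infer:
- *No AE data will exist for usual care.* Not supported. Ad-hoc reporting, the AE and serious-event rules and the withdrawal-visit review remain open in that period. What is missing is scheduled review.
- *The tolerability outcome lacks a needed comparator, or is biased by design.* Not supported. No aided-versus-unaided contrast is planned, so there is no estimate of that kind to bias.
- *Half the participants lose the CNC test at Weeks 2 and 4, because the same asterisk sits on it.* Not supported. The Schedule uses the CNC asterisk to mean testing in both conditions, and a separate starred note on the articulation survey and CNC tests concerns audio recording. This is a symbol used for more than one purpose.
- *The Week 4 asterisk selects the wrong group, because the extension text still reads* "Group 1 (ALD-Aided): Participants will have the device appropriately re-fitted". Not supported. The label is carried over from randomisation, and footnote (2) says that Group 2 is the group reviewed for tolerability at Week 4.
- *Background ear events are frequent.* The protocol gives no short-term rate, and current ear problems that prevent device use are an exclusion.

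The reply does not remove the contradiction. The asterisk and the footnotes agree with each other, so the limit is not a stray mark, and it conflicts with Table 1 and the AE section. Judging causality event by event also depends on events being asked about in time to place their onset.

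**Conclusion.** The point holds as a contradiction in the text with a practical consequence. Followed as written, the visit lists and footnotes leave all 24 planned usual-care person-weeks of the crossover (20 with 10 completers) without scheduled AE review, and leave Group 1 without a guaranteed review between Week 2 and Week 24. Background and post-removal events would be captured unsystematically, which weakens attribution of device-related effects.

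The person-week counts assume the planned 12 participants and nominal visit times. The 22-week gap assumes that the optional contacts are not taken up and that the participant does not withdraw. The conclusion does not depend on any assumed event rate. The gap concerns the four-week crossover only, since all participants are meant to use the device in the extension. It is a consistency and data-collection point for a small descriptive pilot and does not undermine the planned analysis.

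**What to change.** Reconcile the visit lists and Schedule footnotes with Table 1, the AE section and the withdrawal visit:
- Remove the aided-only restriction from the AE review at Weeks 2 and 4, and from the AE part of Schedule footnotes (1) and (2).
- At both visits, ask every participant about the event types listed in the AE section.
- Record the period of onset, and summarise events descriptively by aided and non-aided period.
- Keep the restriction for device-specific items only (tolerability questionnaire, System Usability Scale, technical issues, diary), worded as: participants who were ALD-aided in the preceding two weeks.
- As clean-up, give the CNC audio-recording note its own symbol.

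The cost is a wording amendment and one extra AE question at visits that every participant already attends.

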#### Withdrawal Criteria

Participants have the right to withdraw from the trial at any time without having to give a reason. Participants who choose to withdraw from the trial will be advised that the data collected up to the point of their withdrawal will be retained.

A member of the research team should try to ascertain the reason for withdrawal and document this reason within the participant's medical notes (see withdrawal visit information for further details).

The Investigator may discontinue a participant from the trial at any time if the Investigator considers it necessary for any reason including:

- Participant withdrawal of consent
- Participant loss of capacity to provide informed consent
- Investigator's discretion that it is in the best interest of the participant to withdraw
- An adverse event that renders the participant unable to continue in the trial
- Termination of the trial by the sponsor or funder

If participants are withdrawn from the trial, the information already obtained will be kept. Participants will be advised of this during recruitment and consent.

#### **End of Trial**

The end of trial for each participant will be completion of their End of Trial visit (Week 24).

# **RANDOMISATION AND DATA COLLECTION**

Randomisation for the crossover period of the trial will be managed through REDCAP, a browser-based Electronic Case Report Form (eCRF) system (https://projectredcap.org/about/). Trial data will also be collated via the REDCAP eCRF, including entry of participant reported outcomes directly onto the system (ePROs).

#### Randomisation

A customised allocation list for participant allocation will be created (with provision of examples) and provided to the RECAP team for upload. Participants will be randomised in a 1:1 ratio, using variable length random permuted blocks (of size 2 and 4) in R statistical software by the trial statistician.

#### **Data Management**

Data Collection Tools and Source Documentation Identification

Completed trial consent forms will be held in the combined TMF/ISF. Copies will be held in the participant medical records.

Source data for this trial will consist of annotations in the participant medical records, trial specific researcher assessment tools and worksheets, participant completed questionnaires and diaries (including ePROs recorded via REDCAP), audiology reports issued by NE1Hear and audio recordings of the Atkin & Fisher's Articulation Survey and CNC tests.

Additionally, participants will be required to complete hearing assessments via the relevant software on Newcastle University laptops and computers. Access to the computers will be restricted to authorised members of the study team and will be protected via password.

The tests will be administered to participants by a member of the research team who will be present throughout. The software used does not require identifiable details, therefore participants will not be required to provide their name or enter any identifiable details when undertaking the tests. All participants will be identified on the relevant software via their unique study participant ID.

Where participants remotely enter outcomes directly through REDCAP, they will be sent a reminder link by telephone and/or email to complete self-reported questionnaires. To ensure inclusivity, if participants are unable to utilise the online system, the trial team will work with them to enable completion of data over the telephone, face-to-face, or paper based questionnaires via post.

Completed researcher/clinician assessment tools will be stored in the TMF/ISF. Participants will be identified on any assessment tools via their unique trial ID number rather than by name.

Reports issued by NE1Hear (in the form of PDF documents forwarded to the trial team by secure nhs.net email) will also identify participants by their unique trial ID number. These will be printed on receipt at site and added to the TMF/ISF. Copies will also be added to the participants' hospital records.

Audio recordings of the Atkin and Fisher's Articulation Survey and CNC test will be captured using a digital recording device. Recordings will then be downloaded onto a secure Newcastle University shared drive folder for storage. Once stored, the original recordings will be deleted from the device. Recordings will be pseudo-anonymised and will identify participants by their unique study ID only.

To arrange trial visits, the study team will email (or phone) NE1Hear. The personal identifiable information required to arrange visits (consisting of participant name and screening ID) will be communicated via email, secure internal post, or phone.

Data will be transcribed from the source data directly onto REDCAP (with the exception of the ePRO where RECAP will be the source data). Participants will be identified on REDCAP via their unique trial ID number and DOB (i.e., the trial database will be classed as containing pseudo-anonymised data only). REDCAP will also be utilised for its Alerts and Notifications features, to send alerts to remind participants to complete questionnaires (via email address and /or mobile number).

All efforts will be made to ensure that the data provided in the source documents is as complete as possible. Regular review of data completeness and regular data cleaning activities will be undertaken. These activities may include telephoning participants to obtain missing information. Any activities which involve contacting trial participants will be conducted by delegated members of the site team who are known to the participant (i.e., trial research nurse).

